8.1. Objectives

8.1.1. Primary Objectives

Part A

To identify the maximum tolerated dose (MTD) of bemcentinib in AML patients who have received previous treatment with cytotoxic chemotherapy (with or without hematopoietic stem cell transplantation) or a targeted or biologic agent (e.g. hypomethylating agent, tyrosine kinase inhibitor, antibody), and have relapsed after or have been refractory to treatment with such prior therapy.

Part B

To identify the safety and tolerability of bemcentinib as a single agent in patients with AML or MDS (Parts B1 and B4), or in combination with low dose cytarabine (Part B2 and Part B5) or decitabine (Part B3), in patients with AML who are unsuitable for intensive chemotherapy as a result of advanced age or existing co-morbidities.

8.1.2. Secondary Objectives

Part A

- To identify the Dose Limiting Toxicity (DLT) profile of bemcentinib
- To explore the safety and efficacy of bemcentinib
- To characterize the PK profile of bemcentinib

Part B

- To explore the efficacy of bemcentinib, as a single agent in patients with AML or MDS (Parts B1 and B4)
- To explore the efficacy of bemcentinib in combination with low dose cytarabine (Part B2 and Part B5) or decitabine (Part B3), in patients with AML who are unsuitable for intensive chemotherapy
- To evaluate bemcentinib PK (all Part B cohorts)

8.1.3. Exploratory Objectives

Parts A and B

- To identify and evaluate potential predictive biomarkers, e.g. soluble AXL (sAXL) and other associated soluble biomarkers. Pre-treatment levels of biomarkers will be correlated with clinical endpoints
- To establish the effects of bemcentinib on relevant biological endpoints in peripheral blood (including sAXL peripheral blood mononuclear cells [PBMC] and BM samples)
- To assess pharmacodynamic biomarkers in tissue and blood to support the clinical development of bemcentinib
- To evaluate other biomarkers relevant to the investigational agents for exploratory purposes

8.2. Endpoints

8.2.1. Safety Endpoints

Safety and tolerability will be assessed by conducting the following safety assessments at pre-defined time-points during the study:

- Treatment emergent AEs
- Physical examination
- Vital signs including blood pressure (BP), heart rate (HR), respiration rate and temperature
- Electrocardiogram (ECG)
- Echocardiogram
- Laboratory findings including clinical chemistry, hematology and urinalysis

8.2.2. Efficacy Endpoints

In AML, efficacy endpoints will be measured using the following response criteria.

- Objective Response (OR) or Stable Disease (SD) according to the revised recommendations of the International Working Group (IWG) in AML [Cheson, 2003

and Döhner, 2017] (see Appendix 5). SD is defined as having unchanged disease for at least 3 treatment cycles.

- Proportion of patients with an OR + SD as an estimate of clinical benefit.
- Relapse Free Survival
- Event Free Survival
- Overall Survival
- To explore the correlation between baseline biomarker levels and clinical endpoints

In MDS, efficacy endpoints will be measured using the following response criteria.

- OR or SD according to the revised recommendations of the IWG in MDS (see Appendix 6). SD is defined as failure to achieve at least PR but not evidence of PD for at least 3 treatment cycles.
- Proportion of patients with an OR + SD as an estimate of clinical benefit.
- Relapse Free Survival
- Event Free Survival
- Overall Survival
- To explore the correlation between baseline biomarker levels and clinical endpoints

8.2.3. Pharmacokinetic Endpoints

As a minimum, area under the curve within a dosing interval ($AUC_{0-\tau}$), C_{max} , and time to maximum concentration (T_{max}) for bemcentinib will be determined from plasma. Additional parameters may also be reported, as deemed appropriate once data are reviewed.

8.2.4. Pharmacodynamic and Predictive Endpoints

The effects of bemcentinib on pharmacodynamic endpoints of AXL inhibition will be determined in BM aspirates and blood samples:

- To identify and evaluate potential predictive biomarkers, e.g. sAXL and other associated soluble biomarkers. Pre-treatment levels of biomarkers will be correlated with clinical endpoints

- To establish the effects of bemcentinib on relevant biological endpoints in peripheral blood (including sAXL PMBCs) and BM samples
- To assess pharmacodynamic biomarkers in tissue and blood to support the clinical development of bemcentinib
- To evaluate other biomarkers relevant to the investigational agents for exploratory purposes
- Effect of bemcentinib on AXL, sAXL and phospho AXL (pAXL) and downstream effectors of AXL signaling, such as Akt, pAkt, Erk, pErk, SLFN11, Bcl2, Puma by appropriate methods (e.g. flow cytometry (FCM), western blotting, proteomics, transcriptomics)
- Effect of bemcentinib on gene expression by appropriate methods (e.g. FCM, western blotting, proteomics, transcriptomics, quantitative polymerase chain reaction (PCR), DNA-methylation analysis)
- Effect of bemcentinib on relevant immune cell populations
- Effect of bemcentinib on the spectrum of mutations present within the cancer cell population by genomic analysis
- To explore the correlation between baseline biomarker levels and clinical endpoints

9. Study Design

9.1. Overview

This is a Phase Ib/II, open-label, dose-escalation and cohort expansion study to obtain a preliminary assessment of the safety, tolerability and efficacy of bemcentinib, a small molecule inhibitor of AXL kinase in patients with AML or MDS. The study will be conducted at up to approximately 20 sites in Europe and the US and will be performed in approximately 102 evaluable patients with AML or MDS. Additional countries and sites may be added as required to meet the enrolment needs of the study.

In Part A bemcentinib will be administered as monotherapy in patients with relapsed or refractory AML following previous treatment with cytotoxic chemotherapy (with or without hematopoietic stem cell transplantation) or a targeted or biologic agent (e.g. hypomethylating agent, tyrosine kinase inhibitor, antibody).

In Part B bemcentinib will be administered as a single agent in patients with AML who are unsuitable for intensive chemotherapy (i.e. cytarabine/anthracycline on a 3+7 dose or equivalent) as a result of advanced age and/or existing co-morbidities (Part B1) or in MDS patients who have previously received treatment (Part B4) and a further 3 cohorts of bemcentinib administered in combination with low dose cytarabine (Part B2 and Part B5) or decitabine (Part B3) in patients with AML who are unsuitable for intensive chemotherapy because of advanced age or existing co-morbidities will be investigated

In all parts of the study, AML patients with a matched donor and who are candidates for allogeneic BM transplantation are not eligible to participate.

Bemcentinib will be administered orally according to a daily schedule during continuous 21-day treatment cycles. During Cycle 1, Week 1 ONLY the first 3 doses of bemcentinib may serve as a 'loading' dose.

Dosing will consist of a loading dose of 200 mg administered on Days 1, 2 and 3 followed by a daily maintenance dose of 100 mg. This dose may be escalated as agreed by the SMC to a maximum daily loading dose of 400 mg on Days 1, 2 and 3 followed by a maximum daily maintenance dose of 200 mg.

Patients will be instructed to take bemcentinib on an empty stomach at a similar time each morning when they wake or more than 2 hours after a light meal, with water. To maintain a fasted state, patients should be told not eat or drink anything other than water for at least 1 hour after taking the drug.

BGBC003 v10.0 (US);

In Part A the study will follow a 3+3 design to explore the safety and tolerability of repeat dosing of bemcentinib, and to identify the MTD. A minimum of 6-10 patients will be treated at the MTD or RP2D, as determined by the SMC. Depending upon the results of this phase of the study, the safety and efficacy of bemcentinib may be established in up to 4 disease-specific cohorts in Part B.

Part B1

Single agent bemcentinib will be administered to patients with AML who are unsuitable for intensive chemotherapy (i.e. cytarabine/anthracycline on a 3+7 dose or equivalent) as a result of advanced age and/or existing co-morbidities. In order to be eligible patients should have received at least one line of previous therapy.

Part B2

Bemcentinib will be administered in combination with low dose cytarabine in patients with AML who are unsuitable for intensive chemotherapy as a result of advanced age or existing co-morbidities.

Part B3

Bemcentinib will be administered in combination with decitabine in patients with AML who are unsuitable for intensive chemotherapy as a result of advanced age or existing co-morbidities.

Part B4

[figure not shown]
Single agent bemcentinib will be administered to patients with previously treated MDS (including high risk and intermediate with the exception of deletion 5q MDS).

Part B5

Bemcentinib will be administered in combination with cytarabine in patients with AML who are unsuitable for intensive chemotherapy as a result of advanced age or existing co-morbidities. Patients must have received at least one prior treatment for AML.

Please refer to Figure 5 for an outline of the overall study design.

Figure 5: BGBC003 Study Design

9.2. Study Specifics

9.2.1. Phase I DLT Assessment Period

During the dose-escalation phase (Part A), safety, tolerability, PK, and preliminary clinical activity of bemcentinib will be assessed, and the MTD established, in patients who have received previous treatment with cytotoxic chemotherapy or a targeted or biologic agent (e.g. hypomethylating agent, tyrosine kinase inhibitor, antibody) and have relapsed after or have been refractory to treatment with such prior therapy. Patients receiving an allograft in first remission would be eligible at the time of relapse.

A loading dose (Cohort 1) of 200 mg administered on Cycle 1, Days 1, 2 and 3 followed by a daily maintenance dose of 100 mg during continuous 21-day treatment cycles will be evaluated. This dose may be escalated as agreed by the SMC to a maximum daily loading dose of 400 mg on Days 1, 2 and 3 followed by a maximum daily maintenance dose of 200 mg (see Section 9.2.1.2). At least 3 evaluable patients will be entered per cohort.

9.2.1.1. Dose Escalation Scheme

Initially three patients will be recruited into Cohort 1 and will complete 1 cycle of treatment before a dose-escalation evaluation is made. A patient must receive all loading doses and miss no more than 3 maintenance doses in Cycle 1 in order to be considered as informative to support dose escalation, unless the missed doses are due to bemcentinib toxicity (see Section 9.2.1.2. Dose Limiting Toxicity).

The decision to dose-escalate (or not) will be made by the SMC comprising a representative from each actively recruiting investigational site and a representative of the BerGenBio ASA study team. Minutes of the SMC meeting will be recorded and circulated for final approval before being placed in the Trial Master File (TMF). The decision to dose escalate will be based upon the tolerability of bemcentinib.

Where dose escalation occurs, 3 patients will be recruited to the next cohort (dose level) and will complete 1 cycle of treatment before a dose-escalation evaluation is made, as outlined above.

If one patient in a cohort experiences a DLT during Cycle 1, the cohort will be expanded to 6 patients. If 2 of 3 or 2 of 6 patients in a cohort experience DLT no further dose-escalation will take place and the dose below will be nominated as the MTD. If the starting dose exceeds the MTD, a lower dose may be explored if recommended by the SMC. Provided treatment with the starting dose is considered safe by the SMC according to DLT evaluation, dose escalation may proceed.

Possible dosing levels are illustrated in Table 3. Dosing with Formulation 2 will consist of a loading dose of 200 mg administered on Days 1, 2 and 3 followed by a daily maintenance dose of 100 mg. This dose may be escalated as agreed by the SMC to a maximum daily loading dose of 400 mg on Days 1, 2 and 3 followed by a maximum daily maintenance dose of 200 mg. The maximum daily dose that may be explored in this study will be 400 mg.

Table 3: Possible Bemcentinib Dosing Levels Involving A Loading Dose and Daily Dose for Part A

[figure not shown]
Total Loading Dose over 3 days (mg)	Days 1, 2 and 3 Loading Dose (mg)	Daily maintenance dose (mg)
600	200*	100*
1200	400	200

*starting dose

If a patient withdraws or is withdrawn for reasons other than DLT prior to completing Cycle 1, the patient will be replaced for the purposes of toxicity evaluation.

Please refer to Figure 6 for the operating characteristics of the Dose Escalation process.

Figure 6: The 3+3 Dose Escalation Design

9.2.1.2. Dose Limiting Toxicity

DLT will be assessed during the first 3 weeks of treatment with bemcentinib (Cycle 1), according to the National Cancer Institute (NCI) Common Terminology Criteria for Adverse Events (CTCAE) [NCI CTCAE] version 4 considered unrelated to leukemia progression or intercurrent illness, and defined as any of the following:

- CTCAE Grade 3 or 4 nausea, vomiting, or diarrhea that persists despite maximum prophylactic and supportive care.
- Any other CTCAE Grade 3 or 4 non-hematological toxicity that is considered to be clinically significant and causally related to bemcentinib, excluding isolated changes

in laboratory results if no clinical significance or no clinical sequelae and adequately improve within 7 days.

- Prolonged neutropenia with ANC <500 and platelet count <75000 after Day 42 from the start of treatment in the absence of residual leukemia.
- Treatment discontinuation, inability to administer one or more bemcentinib loading dose, or inability to administer three bemcentinib maintenance doses as a result of bemcentinib-related toxicity.
- Any ventricular arrhythmia.

9.2.2. Part B

Following SMC review of all treatment emergent safety and efficacy data from Part A, up to 14 evaluable patients (up to 20 evaluable patients in Part B5) will be recruited into each of up to five cohorts (Parts B1, B2, B3, B4 and B5). Depending upon the safety profile of bemcentinib observed in Part A the initial starting dose in combination with cytarabine (Part B2) or decitabine (Part B3), may be reduced by a single dose level (i.e. MTD -1) which may be evaluated in at least three subjects before introduction of the MTD or RP2D identified in Part A.

Recruitment into Part B5 will be overseen by the Sponsor's study team or designee. The number of recruitment slots for patients with refractory AML, defined as no hematological response to last AML treatment and/or patients who have received 2 or more prior treatments for AML, will be restricted to 1/3 of the sample size (i.e. no more than 6 evaluable patients). The study team will notify investigators when recruitment restrictions are applied.

AML Treatment Status	Pre-Screening Approval Requirement
One prior treatment for AML and NOT refractory	Sponsor approval not required prior to screening
Two or more prior treatments for AML	Sponsor approval mandatory prior to screening
Refractory AML*	Sponsor approval mandatory prior to screening

* Refractory AML is defined as no hematological response to last AML treatment and/or patients who have received 2 or more prior treatments for AML (see Appendix 5 of Protocol BGBC003: Modified International Working Group Response Criteria in Acute Myeloid Leukaemia [Cheson , 2003, Döhner, 2017])

9.3. Overall Study Duration and Follow Up

The study period will consist of screening, treatment period, Final Study Visit, and follow-up period. The Final Study Visit will occur 28 days after the patient has discontinued study

treatment. All subjects will be followed up for survival after the Final Study Visit unless they withdraw consent or are lost to follow-up. Subsequent anti-cancer therapy for AML or MDS will be reported in the electronic case report form (eCRF)

9.3.1. Screening

Patient eligibility for the study will be determined within 14 days prior to the first dose of study treatment. Screening assessments will be conducted according to the Schedule of Events tables in Section 11.

9.3.2. Treatment

Eligible patients will visit the study site to receive study treatment and protocol-specified procedures according to the relevant Schedule of Events table in Section 11. The treatment period will consist of continuous 21-day treatment cycles of bemcentinib.

Patients will be intensively monitored throughout Day 1 to Day 4 inclusive of Cycle 1, and in addition will attend the clinic on Day 8, and Day 15. Patients will attend the clinic once per week during Cycle 2 and then once per cycle thereafter. All patients will continue to receive bemcentinib or the combination for as long as, in the opinion of the investigator, they continue to derive clinical benefit. When there is unacceptable toxicity, confirmed disease progression in the absence of clinical benefit, or withdrawal of consent, bemcentinib or combination treatment must be discontinued. For patients in the combination arms (Part B2, B3 or B5), if treatment related toxicity requires permanent discontinuation, and the toxicity can be clearly assigned to one of the study treatments, the other study drug in the combination can be continued if it is safe to do so (investigator discretion) in the absence of disease progression or intolerable toxicity. The investigator may also decide to discontinue both study treatments at this time.

9.3.2.1 Dosing patients beyond progression

An important clinical observation in the last decade is that immune activation does not necessarily result in complete cancer regression for all patients, but nonetheless, clinical improvements are observed. In this context and for elderly patients with R/R AML, unfit for intensive chemotherapy and with no alternative treatments available for their disease, achieving stable disease and/or becoming transfusion independent, together with performance status improvement, can be viewed as a positive signal. Thus, where in the investigator's opinion, the patient's disease is considered "clinically stable" with clear improvement in the patient's symptomatology and with no other treatment options available,

other than palliative care, it may be in the patient's best interests to remain on treatment with bemcentinib.

Therefore, patients experiencing disease progression are permitted to continue treatment with bemcentinib where the investigator believes patients may continue to derive clinical benefit from continued treatment.

Clinical benefit in this context is defined as meeting one or several of the following criteria: evidence of disease stabilization after documented initial progression (patient is stably worse), tolerance of drug(s), absence of rapid progression based on peripheral or bone marrow blasts and clinical hematology and clinical chemistry parameters, maintenance of good performance status (PS of 2 or less and not deteriorating], absence of worsening clinical symptoms (i.e., no symptomatic deterioration) and/or improvements in patient's quality of life).

Importantly, the decision to continue treatment must be discussed and agreed by the treating investigator, the patient and the Sponsor. All decisions will be documented in writing. Patients dosed beyond progression will continue to be evaluated for potential clinical benefit and safety. This will not affect the time point of disease progression from the perspective of trial analysis.

9.3.3. Final Study Visit

Patients should return to the study site for the Final Study Visit 28 days after permanent discontinuation of all study treatments.

9.3.4. Follow Up

An AE will be monitored for 28 days after the last dose of bemcentinib although only events considered to be related to treatment need to be recorded in the eCRF between the last administration of bemcentinib and the end of the 28 day follow up period. If bemcentinib-related toxicities continue beyond the follow up period, patients will be followed until all bemcentinib-related toxicities have resolved to <Grade 1, stabilized or returned to baseline. If necessary, follow up monitoring for AEs may be conducted over the telephone.

SAEs with a suspected relationship to bemcentinib will be collected beyond the 28-day follow-up period until the event is resolved to \leq Grade 1, stabilized or returned to baseline.

All patients that have permanently discontinued study treatment for whatever reason must be followed for survival. The investigator or designee must confirm with the patient at the time of the Final Study Visit how the patient will be followed for survival (e.g. contact with family or

health care provider). Survival follow-up must be conducted at least every 3 months by the investigator or designee and the date-of-death reported in the eCRF.

All subsequent anticancer therapy for AML or MDS must be reported in the eCRF.

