FOLLOW UP:	
AEs will be monitored for 28 days after the last dose of study treatment. If bemcentinib-related toxicities continue beyond the follow up period, patients will be followed until all bemcentinib-related toxicities have resolved to ≤Grade 1 or less, stabilized or returned to baseline. Follow up monitoring for AEs may be conducted over the telephone. Serious adverse events (SAEs) with a suspected relationship to bemcentinib will be collected indefinitely.
 
The study will be completed when all patients have completed their final study visit.
 
All patients will be followed for survival after they have permanently discontinued from study treatment at ≤ 3 monthly intervals by the site. Subsequent anticancer therapies for AML or MDS must be collected in the electronic case report form (eCRF).
 
The study will be completed when all patients have an OS event, unless the Sponsor terminates OS follow-up once all patients have discontinued study treatment.

STATISTICAL METHODS	
As this is an early study of bemcentinib only descriptive analysis will be performed on safety data. Preliminary statistical analysis will be performed on objective response rates in Part B.
 
Safety:
 
All safety and tolerability assessments will be based on the safety analysis set (all patients who have received at least one dose of study medication).
 
Efficacy:
 
Efficacy assessments will be based on the safety analysis set.

	
Note: patients treated with bemcentinib beyond disease progression will be followed for the same safety and efficacy assessments as for all other patients enrolled into the study until they are withdrawn from the study. The data for patients treated beyond progression will be presented in both a combined output (with all patients) and also a separate output (to reflect a new period of analysis). All data collected will be included in the study CSR.
 
Pharmacokinetics:
 
Individual and mean bemcentinib plasma concentration-time data will be presented in tabular and graphical form. PK parameters for bemcentinib will be derived from an appropriate PK model will be determined using a non-compartmental analysis. Full details of the PK analysis will be presented in a PK Analysis Plan.
 
Pharmacodynamics:
 
Pharmacodynamic data will be listed and summarized by dose cohort and time point as appropriate.

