15.2. Monitoring and Reporting Events

15.2.1. Adverse Events

Any AE experienced by a patient between signing the informed consent form (ICF) and 28 days after the last administration of bemcentinib is to be recorded in the eCRF regardless of the severity and causality of the event, although only events considered to be related to treatment need to be recorded between the last administration of bemcentinib and the end of the 28-day follow up period. If bemcentinib-related toxicities continue beyond the Follow-up period, patients will be followed until all bemcentinib-related toxicities have resolved to Grade ≤1, stabilized or returned to baseline.

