15.2.2. Serious Adverse Events

Any SAE experienced by a patient between the time of the first administration of bemcentinib and 28 days after the last administration is to be recorded on an SAE Report Form as well as in the eCRF within 24 hours of knowledge by the investigator of its occurrence, regardless of the severity and causality of the event. The exception to this will be patients who experience an SAE due to a Screening assessment. Such events should also be reported and will be recorded in the CSR. SAEs with a suspected relationship with bemcentinib will be collected indefinitely. The SAE Report Form should be e-mailed to the [Syneos](mailto:[contact]) Health Safety and Pharmacovigilance Global Safety Mailbox [contact].

All SAEs that have not resolved by the end of the study, or that have not resolved upon the patient's discontinuation from the study, must be followed until any of the following occur:

- The event resolves
- The event stabilizes
- The event returns to baseline status
- The event can be attributed to agents other than the IMP or to factors unrelated to study conduct
- It becomes unlikely that any additional information can be obtained

Any event requiring hospitalization (or prolongation of hospitalization) that occurs during the course of a patient's participation in a clinical study must be reported as an SAE. Exclusions to this are hospitalizations:

- For pre-scheduled or routine elective procedures (as long as the qualifying condition did not worsen or progress, in the opinion of the investigator, since signing the ICF)
- For social reasons, in the absence of an AE e.g. for respite care
- Due to expected deterioration caused by disease progression

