#### 4.3.4 Follow Up

An AE will be monitored for 28 days after the last dose of BGB324, although only events considered to be related to treatment need to be recorded in the electronic Case Report Form (eCRF) between the last administration of BGB324 and the end of the 28 day follow up period. If BGB324-related toxicities continue beyond the follow up period, patients will be followed until all BGB324-related toxicities have resolved to  $\leq$ Grade 1, stabilised or returned to baseline. If necessary, follow up monitoring for AEs may be conducted over the telephone.

SAEs with a suspected relationship to BGB324 will be collected beyond the 28-day follow-up period until the event is resolved to  $\leq$  Grade 1, stabilized or returned to baseline.

All patients that have permanently discontinued study treatment for whatever reason must be followed for survival. The investigator or designee must confirm with the patient at the time of the Final Study Visit how the patient will be followed for survival (e.g. contact with family or health care provider). Survival follow-up must be conducted at least every 3 months by the investigator or designee and the date-of-death reported in the eCRF.

All subsequent anticancer therapy for AML or MDS must be reported in the eCRF.

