### 5.8.1 Adverse events

The number and percentage of patients reporting TEAEs will be tabulated by MedDRA preferred term and system organ class, and summarized by CTCAE grade also. All AEs commencing prior to dosing with study medication will be excluded from the tabulation but will be fully listed.

A subject with more than one occurrence of the same adverse event in a particular system organ class will be counted only once in the total of those experiencing adverse events in that particular system organ class. If a subject experiences the same adverse event at more than one severity, or with more than one relationship to study drug, the most severe rating or the stronger causal relationship to study drug will be given precedence. Any missing severity, causality, or outcome will not be imputed and classed as unknown.

An overall summary classifying subjects with events according to seriousness, severity, maximum relationship to BGB324, and maximum CTCAE grade will also be presented.

Related events are defined as events that are definitely, possibly or probably related to study medication or with an unknown relationship.

Treatment-Emergent AEs are any AEs that start or worsen after first dose of study drug until 28 days following the last dose. AEs with partial onset dates will be assumed to have the latest possible onset date (while accounting for stop date) for determining treatment emergence, but no formal imputation will be done. AEs that have missing onset dates will be considered to be treatment-emergent, unless the stop date is known to be prior to the first administration of BGB324.

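### All-causality TEAEs are counted to 28 days after the last dose, but unrelated, non-serious events after the last bemcentinib dose may be recorded incompletely and differently by site

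*Protocol*

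**What the plan says.** **Counting rule.** SAP 5.8.1: "Treatment-Emergent AEs are any AEs that start or worsen after first dose of study drug until 28 days following the last dose". There is no causality limit, and the numbers and percentages of patients are tabulated by system organ class and preferred term.

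**Recording rule.** Protocol 9.3.4 says that, from the last bemcentinib dose to the end of the 28-day follow-up, "only events considered to be related to treatment need to be recorded in the eCRF". Protocol 15.2.1 has the same exception ("only events considered to be related to treatment need to be recorded between the last administration of bemcentinib"), and SAP 4.3.4 carries it over ("only events considered to be related to treatment need to be recorded in the electronic Case Report Form (eCRF"). The list of changes from the protocol in SAP 5.14 does not mention the difference between the two rules.

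**Text pointing the other way.** Protocol 15.4 makes investigators responsible for recording every adverse event whatever its relationship to bemcentinib. Section 11.4 lists adverse event recording at the Final Study Visit without a causality limit, and Tables 4 to 6 mark adverse events at End of Study.

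**Serious events.** Protocol 15.2.2 is not limited to related events. Any SAE "between the time of the first administration of bemcentinib and 28 days after the last administration is to be recorded on an SAE Report Form" and in the eCRF, "within 24 hours of knowledge by the investigator of its occurrence, regardless of the severity and causality of the event".

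**Anchor.** The synopsis (Follow Up) says "AEs will be monitored for 28 days after the last dose of study treatment", whereas 9.3.4 and 15.2.1 count from the last bemcentinib dose. SAP 5.8.1 does not name the drug whose last dose is meant.

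**The concern.** Safety and tolerability is the primary objective of Part B, and treatment-emergent events head the list of safety endpoints (protocol 8.1.1 and 8.2.1). If sites use the exception, the all-causality tables join two periods with different ascertainment: full recording on bemcentinib, then related events and SAEs only for up to 28 days. A reader of the tables cannot see the join, and cannot tell which sites followed 9.3.4 and which followed 15.4. Any bias in the all-causality patient rates is downward. It can be largest where treatment is short, because the 28 days are then a larger part of the window.

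In B2, B3 and B5 the partner drug may continue alone (protocol 9.3.2), so the choice of anchor decides whether that time falls under the full or the restricted rule.

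**Working it through.** The plan states no adverse event rate or exposure for this point, so there is no figure to reproduce. The check compares the rules and then gives a scale.

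**1. Which events are exposed.** Cross the counting rule with the recording rules for the 28 days after the last bemcentinib dose:

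| Event after last bemcentinib dose | Counted as TEAE (SAP 5.8.1) | Recording required |
|---|---|---|
| SAE, any cause | yes | yes (15.2.2) |
| Non-serious, related | yes | yes (9.3.4, 15.2.1) |
| Non-serious, unrelated | yes | not under 9.3.4, 15.2.1 and SAP 4.3.4; yes under 15.4 and 11.4 |

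Only the last row is in doubt.

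**2. Which tables are exposed.** These are the all-TEAE tables, the non-serious tables and the non-serious part of the Grade ≥3 tables. The all-causality SAE tables and the bemcentinib-related tables draw only on the first two rows.

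**3. How a rate is affected.** SAP 5.8.1 counts a patient once per event and gives precedence to the worst severity. A rate therefore falls only if the patient's first episode of that term, or the worst one in a table by grade, lies in the 28 days and goes unrecorded. One missed patient lowers a cohort rate by 1/14 = 7.1 percentage points in a cohort of 14 (B1 to B4), or 1/20 = 5.0 points in a cohort of 20 (B5).

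**4. Share of the window under the restricted rule.** Cycles are 21 days (protocol 9.3.2). For *c* cycles of treatment (assumed; the documents give no exposure), the share is 28/(21*c* + 28):

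- 1 cycle: 28/49 = 57%
- 2 cycles: 28/70 = 40%
- 3 cycles: 28/91 = 31%
- 6 cycles: 28/154 = 18%

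Protocol 12.4 recommends at least 3 cycles.

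**5. Illustration on the patient scale.** Assume a constant hazard over the window and that no unrelated, non-serious event is recorded after the last dose. An event with true incidence *p* is then recorded at 1 − (1 − *p*)^(21*c*/(21*c* + 28)). For *p* = 20%:

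- 1 cycle: 1 − 0.8^(21/49) = 9.1%
- 2 cycles: 1 − 0.8^(42/70) = 12.5%
- 3 cycles: 1 − 0.8^(63/91) = 14.3%
- 6 cycles: 1 − 0.8^(126/154) = 16.7%

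Because nothing is assumed to be recorded, this is the extreme case under that hazard, not an estimate.

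**The case against.** The strongest case against has five parts.

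- **The exception is permissive.** It says what need be recorded, not what must be left out, and 15.4, 11.4 and the schedules of events point to recording everything. This stands. A reader might infer that the all-causality rates are under-counted as a matter of fact, but the documents support only that they may be. The conflict is itself the reason to act, because sites hold opposite instructions.
- **Partner-only treatment.** A reader might infer that in B2, B3 and B5 unrelated events go unrecorded while patients are still on cytarabine or decitabine. Protocol 12.5 requires patients who stop one agent to continue all study assessments until all study treatments have stopped, so that gap is not established. The anchor remains unclear. Causality guidance in 15.3.2 refers only to bemcentinib, yet SAP 5.8.1.1 plans tables of cytarabine-related and decitabine-related events.
- **The exposed events are the least informative.** They are unrelated and non-serious, and SAEs of any cause are kept to day 28. This stands and narrows the point.
- **Missing-event percentages.** A reader might multiply the window share by an assumed unrelated fraction and report that share of events as missing. That counts events, whereas the SAP reports patients. It also assumes the exposure, the related fraction, even accrual after dosing stops and no voluntary recording. The documents support none of these.
- **Little depends on it.** The safety analysis is descriptive (protocol 16.4.2), SAP 5.1 plans no comparison of groups, and DLTs are assessed in Cycle 1. This limits the consequence, but the tables are still the main output for Part B's primary objective.

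**Conclusion.** The mismatch is real and stands within the SAP itself, between 4.3.4 and 5.8.1. Unrelated, non-serious events with onset or worsening after the last bemcentinib dose may be incompletely and unevenly recorded, and the three groups of tables named in the working can be biased downward as a result.

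The size of the bias cannot be computed, because the documents give no event rates, no exposure and no indication of which instruction sites followed. The window shares of 57% to 18% for 1 to 6 cycles show how much of the counted time is open to the restricted rule. They are not the fraction of events or patients missed, and they rest on assumed exposure. The correction is worth making because it is cheap and the output serves a primary objective. It does not put the SAE findings or the bemcentinib-related findings in doubt.

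**What to change.** **SAP 5.8.1.**

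- Count unrelated, non-serious TEAEs only to the end of full recording. That is the last bemcentinib dose, or the last dose of any study treatment in B2, B3 and B5 if full recording did continue under protocol 12.5.
- Keep related events and all SAEs to day 28. Ending the whole TEAE window at the last dose would remove collected related events and SAEs from the main table. The mean half-life of 45.6 to 88.7 hours (protocol 7.2.2) is a reason to keep them.
- Show the 28-day post-treatment period in a separate table, and footnote the all-causality tables with the recording rule.

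**Reconciliation.** Bring protocol 9.3.4 and 15.2.1 and SAP 4.3.4 into line with protocol 15.4. State one anchor for B2, B3 and B5: the last bemcentinib dose or the last dose of any study treatment. Extending the unrelated, non-serious count to the last dose of any study treatment without confirming full recording could bring restricted time back in.

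**Cost.** SAP wording, a footnote and one extra table, with no new data. Removing the related-only exception from the protocol would add some data entry and would help only patients still in follow-up. It cannot change the data from Parts A and B3, which protocol 16.8 reports as fully completed.
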